6.5. MONITORING PLAN

Andre Vision and Device Research will monitor the investigation pursuant to ISO 14155:2011, any applicable health authority regulations and the clinical research procedures adopted by the CRO. The clinical monitor will maintain close contact with the Investigators and the Study Coordinators. The Investigator will permit CRO representatives direct access to source data/documents for study-related monitoring, audits, review, and inspection(s). The monitor's responsibilities will include:

- Ensuring that the investigation is being conducted according to the protocol;
- Ensuring the rights and wellbeing of subjects are protected;
- Ensuring that protocol deviations are documented with corrective action plans, as applicable;
- Clarifying questions regarding the study;
- Resolving study issues or problems that may arise;
- Reviewing the study records to ensure completeness and accuracy. Study and patient source document records reviewed will include:
 - The Information and Consent Form
 - Source documentation including consenting, medical history, concomitant medications, and adverse event information as applicable.
 - Study related regulatory documents

Study monitoring will involve the following elements:

- CRO representatives will meet with the investigator(s) and conduct a site visit prior to the enrollment of subjects at the site in order to review the adequacy of the subject population, facilities, and equipment with respect to the needs of the study and to train the investigator to the clinical investigation plan.
- On an ongoing basis CRO representatives will remotely monitor study records and data.
- CRO representatives may visit the clinical site during the study (interim visit) to review study progress and verify source documents if needed.
- Telephone/email consultation will occur as necessary during the course of the investigation to ensure the proper progress and documentation of the study findings.
- CRO representatives will meet with the investigator(s) at the completion of the investigation in order to verify accuracy of data to source documents (when applicable), complete disposition of study materials, and study close out activities.

7. STATISTICAL CONSIDERATIONS

The CRO will manage data analysis and reporting. Subject characteristics and study conduct summaries will be reported—including tables such as a subject disposition table, demographics and baseline characteristics tables (including age, gender, baseline refraction, lens wear experience), summary table of screen failures by reason, accountability of eyes enrolled, and subjects excluded from key analysis sets.

All descriptive summary statistics will be displayed with n and % for categorical data, and with mean, standard deviation, median, minimum, and maximum for continuous data. The unit will be eye. Tables will be presented by treatment and overall. Slit lamp findings will be presented by all study visits, tabulated by eyes and incidence rate for completed test lens group, completed control lens group, discontinued test lens group and discontinued control eyes group. Primary and secondary outcomes will be analyzed by descriptive statistics only. As such, there are no statistical hypotheses to be tested.

Trend analysis profile will be provided following directions provided in the FDA guidance *Premarket Notification [510(k)] Guidance Document for Class II Daily Wear Contact Lenses*. All participants who meet the eligibility criteria, adhere to the protocol, and successfully complete the full study assessment will be available for the per-protocol analysis. Subjects with missing data will be included in the analysis unless there is some non-response-related reason to exclude them, such as a protocol violation/invalid data. Data from all enrolled subjects will be used for reporting of adverse events or other safety related outcomes.

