6.3.2. Exclusion Criteria

Subjects may not be enrolled into the study if ANY of the following apply:

- Currently pregnant or lactating (subjects who become pregnant during the study will be discontinued).
- Any systemic disease, autoimmune disease, or use of medication, which may interfere with contact lens wear. This may include, but not be limited to, diabetes, hyperthyroidism, recurrent herpes simplex/zoster, Sjögren's syndrome, xerophthalmia, acne rosacea, Stevens-Johnson syndrome, and immunosuppressive diseases or any infectious diseases (e.g. hepatitis, tuberculosis).
- The use of systemic or ocular medications that would contraindicate contact lens wear.

- Entropion, ectropion, extrusions, chalazia, recurrent styes, glaucoma, history of recurrent corneal erosions, aphakia, or moderate or above corneal distortion by keratometry.
- Any previous, or planned, ocular or interocular surgery (e.g., radial keratotomy, photorefractive keratectomy (PRK), laser in situ keratomileusis (LASIK), etc.).
- Any grade 2 or greater slit lamp findings for corneal staining, and any grade 3 or greater slit lamp findings for other abnormalities (e.g., edema, corneal neovascularization, tarsal abnormalities, conjunctival injection) on the ISO 11980 classification scale, any current inflammatory events or events within the last 6 months, or any other ocular abnormality that may contraindicate contact lens wear.
- Any known hypersensitivity or allergic reaction to Biotrue or ClearCare contact lens care solutions
- Any ocular infection, allergy or clinically significant ocular disease (e.g. corneal edema, uveitis, severe keratoconjunctivitis sicca, ocular hypertension), or ocular conditions (e.g. strabismus), which might interfere with the study.
- Any corneal distortion resulting from previous hard or rigid gas permeable contact lens wear.
- Extended wear, monovision or multi-focal contact lens correction.
- Participation in any contact lens or lens care product clinical trial within 30 days prior to study enrollment.
- Any subject where the randomized lens demonstrates a fit that is deemed inappropriate by the investigator, including, but not limited to, the lens being too flat, too steep, have excessive or inadequate movement, and/or insufficient limbal coverage.
- Employee or relative of employees of sponsor or investigational clinic (e.g., Investigator, Coordinator, Technician)

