6.3.4. Point of Enrollment

The investigational site will screen subjects to determine if each subject is eligible to participate in the investigation. Pre-screening of basic eligibility may occur prior to the initial visit; however, Subjects are required to complete the informed consent process prior to the baseline/screening visit (Visit 1). All subjects who sign an Informed Consent form and meet the eligibility criteria during the screening visit are defined as “enrolled” into the clinical investigation regardless of any further participation.

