6.3.6. Number of Subjects Required

To ensure a minimum of 50 completed subjects (with 30 completed subjects in the test arm), 75 subjects will be enrolled to participate. Up to fifty (50) subjects will wear the test contact lenses and up to twenty-five (25) subjects will wear the control contact lenses.

The number of subjects was determined based on the recommendations in *Premarket Notification [510(k)] Guidance Document for Class II Daily Wear Contact Lenses*.

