6.4.8. Study Completion Procedures

A study exit form must be completed for all subjects.

Subject Completion:

Subjects are considered to have completed the study if they have completed follow-up examinations through the 91-day study period and when all of the study procedures have been completed. All completed subjects’ data will be considered evaluable unless a significant protocol deviation was reported. Written justification will be required for the use of data in the evaluation of the safety and/or efficacy of study product from any subject found to have a protocol deviation.

Subject Discontinuation:

Possible reasons for discontinuation include:

1. Screen Failure – the subject does not meet the protocol specified inclusion criteria or has one or more of the exclusion criteria present.
2. Adverse Event – the subject has been reported to have an adverse event and was discontinued due to the adverse event.
3. Subject Decision – the subject decides for whatever reason to exit from the study. The reason must be recorded in the comments section of the Exit Form.
4. Investigator, Sponsor or IRB Decision – the subject is exited from the study based on a decision by the investigator the Sponsor or the reviewing IRB. The reason for discontinuation must be recorded in the comments section of the Exit Form.
5. Protocol Violation – the subject or the investigator is repeatedly found to be in violation of the study protocol.

Subjects may be discontinued from the study at the discretion of the investigator only for reasons related to the study treatment regimen that would jeopardize the subjects' health and/or welfare if they were to continue in the study.

Discontinued subjects will be considered to have completed the study and should not be replaced. However, every effort will be made to follow discontinued subjects to obtain as much follow-up data as possible regarding the subject's current visual status until the planned end of the study period.

NOTE: The Investigator will immediately (within 2 working days) notify Monitor/CRO if a subject discontinues from the study.

Subjects Lost to Follow-up:

Subjects may be lost to follow-up from the study for non-treatment related reasons. Reasons for loss to follow-up include, but are not necessarily limited to:

- 1) voluntary withdrawal from the study by the subject;
- 2) subject has moved from the area; or
- 3) subject is unwilling or unable to return for follow-up.

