2 = mild	Single or multiple epithelial infiltrates ≥ 1 mm and < 2 mm in diameter
3 = moderate	Multiple infiltrates ≥ 2 mm and < 3 mm in diameter
4 = severe	Multiple dense infiltrates ≥ 3 mm in diameter

a. Other complications/Findings

Record other findings (ie, pinguecula) on a 5-point scale and its description. List all report.

OD: 0 / 1 / 2 / 3 / 4

OS: 0 / 1 / 2 / 3 / 4

NOTE

0 = none	no other significant biomicroscopic findings
1 = trace	minimal findings such as a tear film abnormality (debris or low tear break up time)
2 = mild	mild findings such as: lens adhesion
3 = moderate	significant findings c. iritis with minimal cells or flare d. conjunctivitis or EKC
4 = severe	severe findings such as: a. iritis with marked cells and/or flare b. corneal or conjunctival infection c. corneal ulcer d. recurrent erosion

Is this subject eligible for the study participation?

Yes No

(Fill out Paper “Inclusion & Exclusion Criterial Checklist”)

If no, submit the form by signing on the last tab and fill out Exit Form.

If yes, perform the rest of procedures.

Dispense Tab

Randomization Group: A / B /C / D

Study Lens Type: Q / V

Care Solution: B / C

Dispense Contact Lens Rx

	Lens Lot #	Rx-Sph (D)	BC (mm)	Diameter (mm)
OD				
OS				
Note				

Insert the study Lens and wait for 5 minutes!

Visual Acuity and Over-refraction with Dispensing Contact Lens

	VA with Dispensing Lens (logMar)	Spherical Over-Refraction (D)	VA with Over-Refraction (logMar)
OD			
OS			
OU		n/a	n/a

Lens Surface / Fitting Tab**Slit Lamp Lens Surface/Fit Assessment****a. Lens Front Surface Wettability**

OD: 0 / 1 / 2 / 3 / 4

OS: 0 / 1 / 2 / 3 / 4

0	A smooth uniformly reflecting wettable surface.
1	A coarse hazy wettable surface which seems resolved momentarily with each blink and becomes exacerbated with staring.
2	One stable dry (non-wetting) area of some magnitude.
3	More than 1 stable dry (non-wetting) area of some magnitude.
4	Non-wettable lens surface of severe magnitude.

b. Lens Front Surface Deposits: Observe under low slit lamp magnification

OD: 0 / 1 / 2 / 3 / 4

OS: 0 / 1 / 2 / 3 / 4

0	Absent, clean surface
1	Very slight, only visible after tear film drying
2	Slight, visible deposits easily removable
3	Moderate, deposits adherent and not removable
4	Severe, non-removable deposits and comfort affected

c. Lens Back Surface Deposits: Observe under low slit lamp magnification

OD: 0 / 1 / 2 / 3 / 4

OS: 0 / 1 / 2 / 3 / 4

0	Absent, clean surface

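### Eye-based descriptive tables give no per-person ocular adverse event risk, no test-control difference and no interval; two added tables would supply all three from data already collected

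*Combined protocol and SAP*

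**What the plan says.** Section 7 sets the unit and layout: "The unit will be eye. Tables will be presented by treatment and overall". The statistics it lists are n and % for categorical data, and mean, SD, median, minimum and maximum for continuous data. It adds: "Primary and secondary outcomes will be analyzed by descriptive statistics only", so no hypothesis is tested. The subject-level summaries it names cover disposition, baseline characteristics, screen failures and exclusions from analysis sets, not the primary outcomes.

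For safety, "Data from all enrolled subjects will be used for reporting of adverse events or other safety related outcomes". Section 14 counts each affected eye as one adverse event and promises that every event will appear in the final report.

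The design is per person. Section 6.1.1 describes a bilateral, parallel-group randomized study, Section 6.4.3 randomizes the subject, and the dispensing form in Appendix 3 has one lens field per subject: "Study Lens Type: Q / V". Section 6.2.2 says the primary outcomes will be tabulated against the control lens, and Section 5 gives substantial equivalence as the purpose.

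**The concern.** Lenses are assigned per subject and worn in both eyes, so every test-control contrast is between people. The quantity the randomized arms can compare is the risk per person, and an eye table does not identify it. How far the per-eye figure falls below the per-person figure depends on how often both eyes are affected. Section 4.2 says infection is almost always one-sided, and for such events the per-eye rate is half the per-person rate.

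By-arm columns can be read side by side, but nothing in them shows how far apart the arms could truly be. A result of no events in either arm could be taken as closer agreement than arms of at most 50 and 25 subjects can show.

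The denominator also needs a sentence. Section 6.3.4 says "All subjects who sign an Informed Consent form and meet the eligibility criteria during the screening visit are defined as" enrolled, which can include people who never had a study lens inserted. Section 6.3.2 excludes "Any subject where the randomized lens demonstrates a fit that is deemed inappropriate by the investigator", yet under Section 6.4.7 fit is examined only after insertion. Someone exposed to the lens could therefore be counted or not, depending on how the two sections are read.

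**Working it through.** **Inputs from the documents.** Up to 50 test and 25 control subjects, that is 100 and 50 eyes (Section 6.3.6). Minimum completers: "To ensure a minimum of 50 completed subjects (with 30 completed subjects in the test arm"). Each affected eye is one event (Section 14). No alpha, power, SD, event rate or dropout rate is given, and the total of 75 is attributed to a guidance document, so there is no precision calculation to reproduce. The counts only imply a tolerated loss of (75 - 50)/75 = 33% overall and (50 - 30)/50 = 40% in the test arm.

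**Assumptions.** The event counts below are illustrative. Between-eye correlation is taken as 0.5 to 0.9 and the acuity SD as 0.05 to 0.10 logMAR. Twenty control completers is 50 - 30; no control minimum is stated.

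**Step 1: per-eye against per-person risk.** If k of n subjects are affected and a share b of them in both eyes, the affected eyes number k(1 + b) out of 2n. The per-eye rate is therefore (k/n) × (1 + b)/2: a factor of 0.50 at b = 0, 0.75 at b = 0.5 and 1 at b = 1. Ten affected eyes of 100 could be:
- 5 of 50 subjects, all bilateral: 10% (exact 95% CI 3.3 to 21.8%)
- 10 of 50 subjects, all one-sided: 20% (exact 95% CI 10.0 to 33.7%)

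The eye table is the same in both cases. If repeat events in one eye are counted, even this identity fails: one test subject with two separate events in one eye is 2.0% of subjects, 1.0% of eyes and 2 events per 100 eyes.

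**Step 2: what the arm sizes can show for adverse events.** With zero events the exact two-sided 95% upper limit is 1 - 0.025^(1/n):
- n = 50: 7.1%
- n = 25: 13.7%

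The Newcombe interval for test minus control uses Wilson limits, which at zero events are z²/(n + z²), with z² = 3.84:
- 3.84/53.84 = 7.1% (test) and 3.84/28.84 = 13.3% (control), so the difference is 0 with interval -13.3 to +7.1 points
- 1 of 50 against 0 of 25: 2.0% (exact CI 0.05 to 10.6%), difference interval -11.4 to +10.5 points
- 4 of 50 against 1 of 25: 8% against 4%, difference 4 points, interval -12.3 to +15.3

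If the last case is all one-sided, the eye table reads 4% against 2%. The ratio is still 2.0, but the difference is 2 points instead of 4.

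**Step 3: visual acuity.** On the two-eye subject mean, unadjusted, the 95% half-width in SD units is t(0.975, n1 + n2 - 2) × √[(1 + ρ)/2 × (1/n1 + 1/n2)].
- 50/25: 1.993 × √(0.75 × 0.06) = 0.42 at ρ = 0.5; 1.993 × √(0.95 × 0.06) = 0.48 at ρ = 0.9
- 30/20: 0.50 to 0.57

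In logMAR at 50/25 this is 0.42 × 0.05 = 0.02 up to 0.48 × 0.10 = 0.05. At 30/20 it is about 0.025 to 0.057.

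**The case against.** The plan is openly descriptive and consistent with having no hypothesis. By-treatment tables do deliver the side-by-side summary that Section 6.2.2 promises. The sentence on the unit cannot be literally universal, since age and discontinuation are per subject, and with at most 75 subjects a count could be derived from the event forms. Trend analysis and event classification defer to outside guidance that might call for subject-level tables. These points stand as reasons to call this an improvement. They do not supply the missing items: Section 7 specifies none of the three, and what the guidance requires cannot be judged from the documents.

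Three stronger readings are tempting, and the documents support none of them.
- A reader might infer that the plan commits a unit-of-analysis error by treating paired eyes as independent. It computes no interval or test, so it makes no false claim of precision. The pairing would matter only if eye-level intervals were added.
- A reader might infer that by-eye acuity means are biased. When both eyes are measured, the mean over eyes equals the mean of the subject means.
- A reader might infer that the trial can exclude little about acuity. On the assumed SDs the half-width is under a third of the 0.2 logMAR worsening flagged on the follow-up form. That flag is for an individual eye, not a margin for a mean difference, but it shows that the wide-interval concern is not established for acuity.

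It is also fair that the plan names neither the visit nor the type of acuity for the primary summary, so those elements of the fix are choices.

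**Conclusion.** The point holds as a worthwhile, low-cost improvement. Followed exactly, Section 7 yields per-eye adverse event figures from which per-person risk cannot be recovered, and arm columns with no difference and no uncertainty, in a study whose lens is randomized per person and whose primary outcomes are to be compared with a control.

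The consequence is mainly for adverse events. Even a clean result at the full 50 and 25 subjects leaves per-person risks of up to 7.1% and 13.7% and differences from -13.3 to +7.1 points compatible with the data. Fewer subjects would widen these limits. For acuity the gain is a stated difference with its interval, probably a fairly narrow one. That rests on the assumed SD and between-eye correlation, and the half-widths are unadjusted while the proposed model adjusts for baseline.

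The added tables would show precision. With no margin stated, they would not by themselves establish equivalence.

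**What to change.** Keep all by-eye tables and add two to Section 7.

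1. **Ocular adverse events by arm.** Number and % of subjects with at least one ocular event, over all randomized subjects in whom a study lens was inserted, including any later excluded for fit. Give an exact 95% CI per arm and the test-minus-control difference with a Newcombe 95% CI. Report separately the enrolled subjects with no lens inserted.

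2. **Visual acuity.** The test-minus-control difference in Day 91 logMAR acuity with the dispensed lenses, with best corrected acuity as a second row. Use a linear model on each subject's two-eye mean, with arm and the two-eye mean of initial-visit best corrected acuity as terms, and a t-based 95% CI. Include everyone with Day 91 data and state the number missing by arm. Do not define the set by completion, because Section 6.4.8 says: "Discontinued subjects will be considered to have completed the study and should not be replaced". Where Day 91 is missing, a sensitivity row may use acuity at discontinuation, but only where the same type of acuity was recorded, since Section 6.4.8 does not say which is taken.

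Cost: a few lines of text and a little more analysis. The event form already holds subject ID, eye and an ocular flag, and both acuities are scheduled at every visit, so the main tables need no new data. The sensitivity row may be sparse. The adverse event intervals will be wide, and the acuity interval covers sampling error but not dropout bias, which is why the missing counts belong beside it. No test, margin or larger sample is needed.

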6.1.2. Measures Taken to Avoid Bias

The assignment to the test or control contact lens and to the lens care system will be randomized to minimize bias. The target subject enrollment will be equivalent for each study site to account for assignment bias.

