Any Lens Parameter Change or Additional Lens Dispense? Yes No

If yes, OD OS OU

Primary Reason for the Parameter Change or Additional Lens Dispense: _____

Secondary Reason for the Parameter Change or Additional Lens Dispense: _____

- Regular lens replacement schedule
- Visual acuity
- Comfort
- Pathology
- Contact lens fit
- Lost
- Torn
- Lens Deposits
- Bad Edge
- Bad Surface / non-wetting
- Other (Specify) _____

New Dispense - Contact Lens Rx

NO DATA

Eye	Lens Lot #	Rx-Sph (D)	BC (mm)	Diameter (mm)
OD				
OS				
Note				

Insert the study Lens and wait for 5 minutes!

Visual Acuity and Over-refraction with New Dispense Contact Lens

	VA with Dispensed Lens (logMar)	Spherical Over-Refraction (D)	VA with Over-Refraction (logMar)
OD			
OS			
OU		n/a	n/a

Study Lenses Collected/Returned? Yes No

(Complete Study Product Dispensing and Accountability Log on Trial Master File)

Study Product Supplied (Day 30, Day 60, and Unscheduled)? Yes No

(Complete Study Product Dispensing and Accountability Log on Trial Master File)

Any Adverse Events to be Reported? Yes No

(If Yes, fill out the Adverse Event Form and contact to CRO accordingly)

Any Protocol Deviation? Yes No

(If Yes, fill out the Protocol Deviation Report and contact to CRO accordingly)

Any Device Deficiencies to be Reported? Yes No

(If Yes, fill out the Device Deficiency Report and contact to CRO accordingly)

Is subject Exit the study? Yes No

(If Yes, fill out Exit form and collect all study lenses)

I am accepting the data pertaining to this subject to be complete and accurate.

Date: ____/____/_____ (MM/DD/YYYY)

Time: ____:____ (HH:MM, 24h)

Investigator Printed name of the signer _____

Signature _____

CONFIDENTIAL

Exit Form

CONFIDENTIAL

Exit Form

Subject ID: _____

Date: ____/____/_____(MM/DD/YYYY)

Principal Investigator: _____

Clinical Investigator: _____

Did the subject complete the study? Yes No

At which visit was the patient exited from the study treatment?

Dispense / Day 7 / Day 14 / Day 30 / Day 60 / Day 91 / Other
(details _____)**Reason for Exit from Study *(multiple choice)***

- Completed Visit Schedule
- Patient Decision (Disinterest)
- Investigator Decision
- Lost to Follow up
- Poor Visual Acuity
- Positive Slit Lamp Finding
- Adverse Reaction
- Lens Positioning
- Discomfort
- Handling Problem
- Other (specify) _____

I am accepting the data pertaining to this subject to be complete and accurate.

Date: ____/____/_____-

Time: ____:_____(24hr)

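### The one slit-lamp layout that Section 7 specifies splits eyes by completion, a status a slit-lamp finding can cause; a table by randomized lens arm of eyes and subjects ever affected should be added

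*Combined protocol and SAP*

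**What the plan says.** Section 7 (Statistical Considerations) presents slit-lamp findings at every study visit, by eye and as an incidence rate, for "completed test lens group, completed control lens group, discontinued test lens group and discontinued control eyes group". No other slit-lamp layout is named.

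The same section has three general statements that bear on this:
- "Tables will be presented by treatment and overall", placed just before the slit-lamp sentence.
- "Data from all enrolled subjects will be used for reporting of adverse events or other safety related outcomes", at the end of the section.
- "As such, there are no statistical hypotheses to be tested", because primary and secondary outcomes are analyzed descriptively.

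Section 6.1.2 relies on random allocation: "The assignment to the test or control contact lens and to the lens care system will be randomized to minimize bias".

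Two places show that a finding can lead to exit. The Exit Form in Appendix 3 offers "Positive Slit Lamp Finding" among the reasons for leaving. Section 6.4.8 defines discontinuation for an adverse event as the case where "the subject has been reported to have an adverse event and was discontinued due to the adverse event". Section 6.4.8 also asks for a slit-lamp examination at the time of discontinuation, so exiting eyes should have data.

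The word completed is not used consistently. Section 6.4.8 first ties completion to follow-up through the 91-day period, then says "Discontinued subjects will be considered to have completed the study and should not be replaced". Section 7 treats completed and discontinued as separate groups.

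**The concern.** The columns of the slit-lamp table are partly set by the outcome being tabulated. If findings make exit more likely, eyes with findings move out of the completed columns, and they do so in greater number in the arm with more findings. The completed-test and completed-control columns then look more alike than the randomized arms do. The study is meant to support substantial equivalence, so a shift toward no difference favours the sponsor's aim.

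The discontinued columns do show the eyes that left, but they will be small. A reader is likely to look first at the large completed columns. With no test or model planned, what the reader concludes depends on which columns and denominators are displayed.

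**Working it through.** **Inputs from the documents.** Up to 50 test and 25 control subjects: 50 + 25 = 75 enrolled. At least 50 are to complete, 30 of them in the test arm (Section 6.3.6). The plan thus tolerates attrition of 1 − 50/75 = 33% overall and 1 − 30/50 = 40% in the test arm, so the completed/discontinued split need not be trivial. The documents state no expected slit-lamp incidence and no exit rate; those below are assumptions.

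**Formulas.** Let p be the proportion with a finding at any visit, q the probability of exit given a finding, and r the probability of exit given none. One unit per subject is used for simplicity.
- Completed cell: p(1 − q) / [p(1 − q) + (1 − p)(1 − r)]
- Discontinued cell: pq / [pq + (1 − p)r]

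**Main illustration.** p = 15% test and 5% control (a 10-point difference), q = 50%, r = 8%.
- Completed test: 0.075 / (0.075 + 0.782) = 8.8%
- Completed control: 0.025 / (0.025 + 0.874) = 2.8%. Difference: 6.0 points.
- Discontinued test: 0.075 / (0.075 + 0.068) = 52%, in about 50 × 0.143 = 7 subjects
- Discontinued control: 0.025 / (0.025 + 0.076) = 25%, in about 25 × 0.101 = 2.5 subjects

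**Range.** Completed-cell difference in points, where the randomized difference is 10:

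| q | r = 8% | r = 15% |
|---|---|---|
| 30% | 8.0 | 8.5 |
| 50% | 6.0 | 6.4 |
| 70% | 3.8 | 4.0 |

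A second set of assumptions (20% against 8%, r = 10%, randomized difference 12.0) behaves the same way:

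| q | Completed cells | Discontinued cells |
|---|---|---|
| 10% | 12.0 | 12.0 |
| 25% | 10.5 | 20.6 |
| 50% | 7.6 | 25.3 |
| 80% | 3.4 | 25.6 |

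When a finding does not change the chance of exit (q = r = 10%), nothing is understated. With equal true rates and equal exit probabilities in both arms, no cell shows a difference.

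**Can the cells be added?** If each eye is classed once as ever or never affected, yes: in the main illustration, 0.075 + 0.075 = 0.15 for test and 0.025 + 0.025 = 0.05 for control. But Section 7 tabulates by visit. Take three hypothetical eyes in one arm: one has a finding at Day 7 and exits; one has findings at Days 7, 14 and 30; one has a finding at Day 60. The counts at Days 7, 14, 30, 60 and 91 are 2, 1, 1, 1 and 0. Their sum is 5, the largest single count is 2, and the number of eyes ever affected is 3. Adding completed and discontinued cells gives the arm's count at each visit. It gives neither the 3 nor the worst grade reached.

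**The case against.** The strongest reply is that the plan already covers this. The general rule "Tables will be presented by treatment and overall" sits directly before the slit-lamp sentence, so the four groups may be extra detail on top of a by-arm table. All enrolled subjects are used for safety outcomes. No eye is excluded: the discontinued columns are displayed, categorical data carry n and %, and by-visit arm counts follow by addition. In the main illustration a reader of the full table would see 52% against 25% among discontinued subjects, which exposes the selection. Findings serious enough to cause exit will often be adverse events as well: Section 14 names staining of grade 3 or more, neovascularization of grade 2 or more, symptomatic infiltrative events and ocular events needing intervention. Discontinuations with reasons are themselves a secondary outcome.

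Much of this stands. A reader might infer that slit-lamp findings are compared only within completion groups, or that findings in exited eyes are lost. The documents support neither: the by-treatment rule may apply, and the discontinued cells keep those eyes. Nor is there a formal test-control comparison of slit-lamp findings to be biased. They are not a listed outcome in Section 6.1.3, Section 6.2.2 promises comparison with the control for the primary outcomes, and the analysis is descriptive throughout.

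Three things remain:
- Section 7 does not say that the general rule covers slit-lamp findings, and the specific sentence that follows sets a different layout. The all-enrolled rule fixes a population, not a layout.
- By-visit cells cannot give the proportion ever affected. This limit would also apply to a by-visit table without the completion split, so it is a reason for the form of the added table rather than evidence of selection.
- Lower grades, such as grade 2 staining or redness and edema that need no intervention, are not named among the significant adverse events. For them the slit-lamp tables are the main summary.

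**Conclusion.** The concern holds in a limited form. Section 7 specifies one slit-lamp layout, and it conditions on a status that a finding can cause. The completed columns read alone are not a comparison of randomized arms and can understate a lens difference. The effect is moved between cells rather than lost, but by-visit cells do not let a reader recover the proportion ever affected.

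On the first set of assumptions, a 10-point difference appears as 3.8 to 8.5 points among completers; on the second, 12.0 points appears as 3.4 to 12.0. These figures rest wholly on assumed incidence and exit rates, and on the exit probabilities being the same in both arms. They show direction and plausible scale, not an expected bias. This is an improvement that should be made, not a flaw that invalidates the plan.

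**What to change.** Keep the four-group tables. Add to Section 7 one slit-lamp table by randomized lens arm:
- Denominator: all subjects, and all eyes, dispensed a study lens.
- Content, for each finding: the n and % with it at any post-dispensing visit (scheduled, unscheduled or exit), and the worst grade reached.
- A statement that descriptive test-control remarks on slit-lamp findings use this table, with the completed/discontinued split as supplementary.

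Also reconcile the meaning of completed between Sections 6.4.8 and 7, and state the definition that the four-group tables use.

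The cost is a few sentences and one table. Slit-lamp data are already collected at every scheduled visit and at discontinuation, so no new subjects, visits or procedures are needed.
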